**A Comparative Study between two approaches of
ultrasound-guided transmuscular quadratus
lumborum block on post-operative analgesia after
total hip arthroplasty.**

**DOCUMENT DATE (DATE OF APPROVAL OF TANTA ETHICAL
COMMITTEE) (34800/7/21) on 25/07/2021**

Introduction

The demand for total hip arthroplasty (THA) continues to increase, with the obvious goals of improving physical function. However, THA is associated with significant post-operative pain, which remains a serious concern for patients (1, 2). Further, post-operative ambulation may be delayed by poorly treated post-operative pain, increasing the risk of pulmonary complications and venous thrombosis(3).

Effective postoperative pain management can improve patient comfort, increase patient satisfaction, promote earlier mobilization and ensure early participation in rehabilitation. Otherwise, patients may suffer chronic pain and disability, with a poor quality of life(4).

Multimodal analgesia including opioids, nonsteroidal anti-inflammatory drugs, patient-controlled analgesia, and regional anesthesia (5, 6) have been shown to reduce pain and opioid consumption after THA (7). Regional anesthetic techniques provides dense analgesia, decrease opioid related side effects (nausea, vomiting, sedation, itching, urinary retention, respiratory depression) by decreasing reliance on opioid medications and decrease pain scores compared with systemic analgesia alone (8, 9).

Quadratus lumborum block (QLB) is a fascial plane block where local anesthetic is injected into the fascial plane around the quadratus lumborum muscle(10). QLB was initially reported for postoperative pain control by Blanco in 2007 (11).It initially described as an analgesic modality for

abdominal surgery. Depending on the needle tip positioning in relation to quadratus lumborum muscle and local anesthetic (LA) injection location, there are several QLB variations using anterior (transmuscular), lateral (QL1), and posterior QL (QL2) approaches (12).

Transmuscular (anterior) QL block involves injection in the plane between the psoas major (PM) and the QL muscles. Cadaveric studies have reported spread of the injectate to the somatic nerves in the thoracic paravertebral space, as well as the spinal nerve which runs anterior to the QL muscle(13-15).

Previous studies have shown that QL1 and QL2 blocks may generate analgesia from T7 to L1, and the transmuscular block(QL3) may cause caudal spread to the L2–L3 dermatomes (16). Thus, the QL3 approach may be more suitable for hip surgery than the other approaches. (17, 18). Recent evidence of the anterior QL block performed at the L3–L4 level in cadavers has shown spread to branches of the lumbar plexus(19, 20), which may account for the analgesia observed after hip surgery(16, 21).

Paraspinous Sagittal Shift QL block is a modification of the anterior QL block, done at L4 transverse process level in a sagittal orientation, involving a craniocaudal approach of LA injection between the QL and PM muscles just after piercing QL fascia. This may allow LA spread behind the anterior thoracolumbar fascia (ATLF) at the level of L4. This approach may achieve better caudal spread to the nerves covered with the fascia iliaca, with a potential for medial spread to the ventral rami of L2 and L3, in addition to a possibility of blocking the nerves passing anterior to the QL muscle, including subcostal, ilioinguinal and iliohypogastric nerves (22).

Aim of work

The aim of this study is to compare between the post-operative analgesic effect of two approaches of transmuscular quadratus lumborum block (transverse versus paraspinous sagittal transmuscular QLB) in total hip replacement surgery.

The primary outcome of this study is the postoperative morphine consumption. Secondary outcome will be the postoperative pain score which will be assessed by visual analogue scale (VAS).

Patients and methods

This prospective, randomized, controlled double blind study will be carried out at Tanta University Hospital on 75 patients scheduled for total hip replacement surgery for a period of one year from September 2021 to August 2022 after approval of institutional ethical committee, and obtaining written informed consent from each patient.

All data of patients will be confidential with secret codes and private file for each patient. All given data will be used for the current medical research only. Any unexpected risks appeared during the course of the research will be cleared to the participants and ethical committee on time and managed.

*NOTE (The study Protocol was approved from Tanta ethical committee with approval number (34800/7/21) on 25/07/2021.

Every patient will receive an explanation to the purpose of the study and have secret code number to ensure privacy to participants and confidentiality of data, an informed written consent will be taken from all patients.

Inclusion criteria:

75 patients, aged between 21- 80 years old, of both sex ASA I - III scheduled for total hip replacement surgery.

Exclusion criteria:

- Patient refusal.

- Coagulopathy
- Spinal deformities
- Peripheral neuropathy; sensory disorders in the leg requiring surgery and chronic pain.
- Mental dysfunction, psychiatric illnesses and cognitive dysfunction.
- History of drug abuse & chronic analgesic use
- History of allergy to local anesthetic.
- Local skin infection at the site of block.
- Body Mass Index $>40\text{Kg/m}^2$.
- Patients with severe cardiac disease, liver disease or renal dysfunction.

Preoperative preparation:

Preoperative assessment will be done by:

History taking, clinical examination, routine laboratory investigations including: CBC, coagulation profile, random blood sugar, renal function test.

During the preanesthetic assessment, all patients will be educated about the visual analogue scale (VAS) for pain assessment, with scores ranging from 0 to 10 (0 represent no pain, while 10 represent maximum intolerable pain).

The patients will be randomly classified into three equal groups (25 patients each). Group allocation will be done by computer generated random numbers and closed opaque sealed envelopes. The study will be designed to be double blind as all patients and postoperative assessor will be blinded to group assignment.

Patients will be randomized to one of three equal groups:

- Group I: Control group (n= 25 patients): Patients in this group will receive ipsilateral sham ultrasound-guided block via subcutaneous injection of 1 ml of normal saline after surgery.
- Group II (n= 25 patients): Patients in this group will receive an ipsilateral single shot of transverse transmuscular approach of QLB (30 ml of plain bupivacaine 0.25%) after surgery using ultrasonographic guidance.
- Group III (n= 25 patients): patients in this group will receive an ipsilateral single-shot of paraspinous sagittal approach of QLB (30 ml of plain bupivacaine 0.25%) after surgery using ultrasonographic guidance.

Intraoperative:

On arrival of the patient to operating room, an intravenous access will be established with intravenous cannula and starting routine monitoring (pulse oximetry, electrocardiogram and noninvasive blood pressure).

Spinal anesthesia will be the anesthetic choice in sitting position and under complete aseptic conditions. Local anesthetic skin infiltration with 3 ml lidocaine 1% at intervertebral space will be done then spinal anaesthesia will be performed using a 25-gauge spinal needle. Once intrathecal placement will be confirmed, a mixture of 2.5 ml of hyperbaric bupivacaine (12.5 mg) and 0.5 ml of fentanyl (25 µg) will be injected. Moreover, sensory and motor blockade will be assessed. Oxygen will be provided to the patient through a nasal canula at a flow rate of 3 L/min.

Blockdescription:

Technique of transverse transmuscular quadratus lumborum block(23):

At the end of the surgery, with the patient in a lateral decubitus position and under antiseptic precautions, the block area will be sterilized with povidone-iodine, a curvilinear ultrasound transducer (2–5 MHz) will be placed transverse to the abdominal flank in the anterior axillary line above the iliac crest to clearly visualise the three abdominal muscle layers. Then, the probe will be moved posteriorly with the external oblique and the internal oblique muscles disappearing into aponeurosis and the latissimus dorsi appearing with the QL muscle beneath. By moving the probe farther posteriorly, the transverse process of the lumbar vertebra, QL, PM and erector spinae muscles identified as a ‘Shamrock sign’. After subcutaneous local infiltration with 3 ml lidocaine 1%, the needle will be inserted using the in-plane technique from the posterior end of the ultrasound probe through the back muscles and then will be advanced through the QL muscle (transmuscular approach), targeting the fascial plane between the QL and PM muscles. The right needle tip position will be confirmed by injection of 1-2 ml of normal saline solution that spread between the quadratus lumborum and psoas major muscles, then the local anaesthetic (30 ml of plain bupivacaine 0.25%) will be injected in the Group II(transverse trans muscular QL group).

Technique of paraspinous sagittal approach of QLB(22):

With the patient in lateral decubitus and the block side independent, and under antiseptic precautions the block area will be sterilized with povidone-iodine, a curvilinear ultrasound transducer (2-5 MHz) will be directed caudally in a sagittal plane 3-4 cm lateral to the lumbar spinous process of L4, which is almost opposite to the iliac crest, producing a longitudinal scan of the lumbar paravertebral region; and thus identifying

the transverse processes of L3 and L4, with PM muscle in-between and erector spinae muscle posteriorly.

The probe will be shifted slowly to the lateral side until the transverse processes disappear and the QL muscle is evident in its long axis attached caudally to the iliac crest with a characteristic sonographic image of three muscle layers appearing from posterior to anterior as: erector spinae, QL, and PM muscles respectively. Here, anterior thoracolumbar fascia which is considered as continuation of fascia transversalis is seen separating QL and PM muscles.

After subcutaneous local infiltration with 3 ml lidocaine 1% at the cephalic end of the probe, the block needle will be advanced in a cephalo-caudal direction, through the erector spinae and QL muscles, until it pierces the QL. 30 ml of bupivacaine 0.25% will be injected anterior to the QL muscle, observing its spread in a caudal direction towards the iliac crest between the QL and psoas muscles.

Technique of sham block:

Subcutaneous injection of 1 ml sterile normal saline will be performed in the control group at the same area using ultrasound transducer pressure that will be intended to simulate a real block procedure (24).

Postoperative:

Postoperative pain will be assessed by the VAS (score for the severity of pain in the range 0–10, where 0 = no pain and 10 = severe pain) at 2,4,6,12,18,24 hours. If the VAS is 4 or more, 3 mg of intravenous morphine will be given as a rescue analgesia. All patients will receive paracetamol 1g intravenous infusion every 6 h and ketolac 30 mg every 12h.

Measurements:

All measurements will be recorded by an investigator who will not be aware about the study design or intervention.

- Demographic data (Age, sex and weight)
- Postoperative pain will be assessed by VAS (score for the severity of pain in the range 0–10, where 0 = no pain and 10 = severe pain) at 2,4,6,12,18,24 hours. If the VAS is 4 or more, 3 mg of intravenous morphine will be given as a rescue analgesia.
- Total Morphine consumption in the first 24 h of the post-operative period will be recorded.
- Time of first analgesic request.
- Incidence of post-operative complications during the first 24 hours will be recorded such as nausea and vomiting, bradycardia, hypotension, pruritus, manifestations of local anesthetic toxicity (cardiac dysrhythmias, convulsions, respiratory depression) will be recorded.
- Patient satisfaction using subjective 5-level scale (1: not satisfied at all, 2: only slightly satisfied, 3: partly or somewhat satisfied, 4: fairly satisfied, 5: perfectly satisfied).

After our study measurements will be complete, the study will be discontinued.

Sample size calculation:

Based upon previous study(23), sample size calculation revealed that at 25 patients will be required in each group to detect a significant change in the postoperative morphine consumption of 2.9 mg at alpha value 0.05 and 80% power of the study.

References

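### The VAS is taught before surgery but no preoperative score is recorded, so baseline pain can be neither described nor adjusted for; the comparison stays unbiased, and the loss is possible precision

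*Protocol*

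**What the plan says.** Under Preoperative preparation the work-up consists of "History taking, clinical examination, routine laboratory investigations including: CBC, coagulation profile, random blood sugar, renal function test". The protocol then adds that, at the preanesthetic assessment, "all patients will be educated about the visual analogue scale". This is instruction in the scale; no score is taken.

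The Measurements list has one baseline line, "Demographic data (Age, sex and weight". The VAS entry there repeats the one under Postoperative: a 0 to 10 score "where 0 = no pain and 10 = severe pain) at 2,4,6,12,18,24 hours". There is no time-zero or preoperative reading.

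On outcomes, Aim of work states: "The primary outcome of this study is the postoperative morphine consumption", followed by "Secondary outcome will be the postoperative pain score which will be assessed by visual analogue scale (VAS". The two are linked by the rescue rule: "If the VAS is 4 or more, 3 mg of intravenous morphine will be given as a rescue analgesia".

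**The concern.** The choice of covariates can be left to an analysis plan, but the collection of the data cannot. The protocol's measurement list decides what will exist, and a pain score not taken before surgery cannot be recovered later. The block is given at the end of surgery, so every recorded VAS comes after the randomised intervention and none can serve as a baseline.

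A preoperative VAS would be a baseline on the same scale as the secondary outcome. Its link to the primary outcome is indirect but real, because morphine is triggered by the VAS. Age, sex and weight do not measure pain. At stake are a possible gain in precision, in a trial that recruits exactly the 25 per group its calculation asks for, and the ability to show whether the arms started with similar pain.

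**Working it through.** **Inputs from the protocol (Sample size calculation):** 25 per group, a difference of 2.9 mg, alpha 0.05, power 80%.

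**Inputs not in the protocol (assumptions):** a two-sided test; the SD of 24 h morphine; the correlation r between preoperative VAS and 24 h morphine, taken from 0 to 0.5.

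**1. The plan's own figure.** The stated 25 per group cannot be confirmed or refuted, because no SD is given. Solving backwards with the normal approximation:

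SD = 2.9 × √(25/2) / (1.960 + 0.842) = 3.66 mg.

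The t-test version gives 3.59 mg, hence about 3.6 mg. Other readings of alpha imply other values: 4.12 mg for a one-sided 0.05, and 3.33 or 3.17 mg with Bonferroni correction for two or three comparisons.

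**2. Power with the covariate.** The residual SD is SD × √(1 − r²). Because the SD was chosen to give 80% at r = 0, it cancels:

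power = Φ(2.802/√(1 − r²) − 1.960), and the equivalent unadjusted n per arm is 25/(1 − r²).

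At r = 0.3: 2.802/0.954 − 1.960 = 0.977, and Φ(0.977) = 83.6%; 25/0.91 = 27.5.

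**3. Cost of adjustment.** In a two-arm comparison the covariate takes one degree of freedom (48 to 47), and expected covariate imbalance inflates the variance by about 1 + 1/(50 − 4) = 1.022. Using the t-test SD of 3.59 mg and the noncentral t distribution gives the last column.

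| r | Variance removed (r²) | Power, no cost | Equivalent n per arm | Power, net of cost |
|---|---|---|---|---|
| 0 | 0% | 80.0% | 25.0 | 79.1% |
| 0.1 | 1% | 80.4% | 25.3 | 79.5% |
| 0.2 | 4% | 81.6% | 26.0 | 80.7% |
| 0.3 | 9% | 83.6% | 27.5 | 82.7% |
| 0.4 | 16% | 86.4% | 29.8 | 85.6% |
| 0.5 | 25% | 89.9% | 33.3 | 89.2% |

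The cost is about 0.6 to 0.9 points throughout, so at r of 0.1 or below there is no net gain.

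**4. Chance imbalance.** For two arms of 25, the standard error of the difference in mean baseline VAS is √(2/25) = 0.28 baseline SD. The 95% range is 1.96 × 0.28 = ±0.55 SD.

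A gap at that edge would shift the morphine difference by r × 0.55 × 3.59 mg: about 0.4 mg at r = 0.2, 0.6 mg at r = 0.3 and 1.0 mg at r = 0.5, against a target of 2.9 mg.

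**The case against.** The strongest reply is that nothing here is wrong. Both outcomes are postoperative, the VAS teaching serves the postoperative readings, and the protocol promises neither a change from baseline nor an adjusted analysis. Randomisation makes the unadjusted comparison valid, and its standard error already allows for chance imbalance. All of this stands, and it confines the point to a low-cost improvement.

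The benefit also depends on an r that the documents do not give. The exclusion of chronic pain and of chronic analgesic use may narrow the spread of preoperative pain and so lower r. Morphine comes in 3 mg steps on top of scheduled analgesics, so the formula for a continuous, linear relation is idealised. Pain from the diseased hip is not the same thing as pain after surgery. These objections stand too, and they are why the range must start at r = 0.

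The reply that covariates belong to the analysis plan stands only in part. Whether and how to adjust belongs there; whether the score exists at all is settled by the protocol.

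A reader might infer more than the documents support:

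- **That the result would be biased.** It would not, because allocation is random.
- **That a material imbalance is likely.** The range of ±0.55 SD is ordinary randomisation error, and its effect on morphine is scaled down by r.
- **That preoperative VAS is the most direct baseline for morphine use.** That is fair for the pain score, but for morphine the link runs only through the rescue rule.

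**Conclusion.** The gap is real but minor. The protocol collects no baseline pain score, and no later plan can supply one. The primary comparison is not invalid and the trial is not shown to be underpowered; the loss is possible precision and a descriptive check on balance.

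For morphine, the net effect of adjusting runs from slightly negative (about 79% power at r = 0) through roughly 3 points gained at r = 0.3 to about 9 points at r = 0.5. The low end is plausible given the exclusions and the 3 mg steps. These figures assume a two-sided 0.05 test, a back-solved SD of about 3.6 mg and an r that the documents do not state. For the VAS comparisons the case is more direct, since baseline and outcome share a scale, but the documents give no figures from which to size that gain.

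**What to change.** Under Preoperative preparation, state that one VAS score is recorded when the scale is taught, before allocation. Add it to the baseline line under Measurements, so that the VAS comparisons and the 24 h morphine comparison can be adjusted for it as a prespecified covariate and the arms can be described on it.

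The cost is one number per patient at a contact that already takes place, one data field and one degree of freedom, with possibly little return for morphine. No treatment, rescue rule or visit changes.
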